Specific Aim: The purpose of the current study is to examine whether high dose N-acetylcysteine (NAC) blocks the adverse effects of increased kynurenic acid (KYNA) on selected measures of brain chemistry, function and behavior, through the inhibition of kynureine aminotransferase (KAT) II, which converts kynureine to KYNA. The study will be a double-blind, placebo-controlled, randomized cross-over challenge study, in which people with schizophrenia are pretreated with either high-dose NAC, 140 mg/kg up to a maximum of 15 g, or placebo, then receive tryptophan (TRYP), 6 gms. The tryptophan challenge method robustly increases peripheral measures of kynureine and KYNA in humans and putatively increases brain KYNA levels, through the CNS conversion of kynureine to KYNA; a process that is observed in both rodents and nonhuman primates. We will evaluate the ability of NAC to inhibit the conversion of kynureine to KYNA with the following primary outcome measures: 1) we will measure serum kynureine and KYNA before and after NAC/placebo pre-treatment and TRYP administration and examine whether NAC compared to placebo blocks the peripheral conversion of kynureine to KYNA; 2) we will use the arterial spin labeling (ASL) technique to measure whole brain and frontal gray matter cerebral blood flow (CBF) before and after NAC/placebo pre-treatment and TRYP administration and examine whether NAC compared to placebo attenuates the effects of TRYP on ASL CBF measures; 3) we will use magnetic resonance spectroscopy (MRS) to measure glutamate and glutathione levels in the medial prefrontal cortex (mPFC) before and after NAC/placebo pre-treatment and TRYP administration and examine whether NAC compared to placebo increases MRS glutathione and glutamate measures; and 4) we will use diffusion tensor imaging (DTI) to measure white matter fractional anisotropy (FA) before and after NAC/placebo pre-treatment and TRYP administration and examine whether NAC compared to placebo increases white matter FA.

We will have two secondary endpoints. First, if we observe that NAC attenuates the effects of TRYP on ASL and/or increases mPFC glutamate levels or white matter DTI FA, then we will examine whether these effects are related to changes in cognitive measures of attention, verbal and visual memory, and working

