memory. Second, we will examine the relationship of serum KYNA levels and kynurenine 3-monoxygenase (KMO) gene polymorphisms to the observed effects of NAC on our neuroimaging and cognitive outcome measures.

We hypothesize that NAC will inhibit KAT II, which will be reflected in the: 1) decreased peripheral conversion of kynurenine to KYNA; and 2) increased CBF, glutamate, and white matter fractional anisotropy (FA). In addition, we hypothesize that the NAC effects on the neuroimaging measures will be related to improved performance on cognitive measures of attention, verbal and visual memory and working memory. These observed effects of NAC will be greater than those seen with placebo. We further hypothesize that the NAC effects on ASL CBF, glutamate, and FA measures will be independent of NAC-induced changes in MRS glutathione, i.e., not due to the NAC oxidative stress mechanism, but, rather, will be correlated with NAC-induced reductions in the peripheral conversion of kynurenine to KYNA. Finally, we hypothesize that the observed effects of NAC on CBF, glutamate, and FA will be related to baseline serum KMO activity and KYNA levels. The demonstration that NAC reverses the adverse impact of increased KYNA levels will importantly support the development of KAT II inhibitors for the enhancement of cognition in schizophrenia.

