Cognitive Assessments: The following cognitive assessments will be used to assess the effects of NAC-induced KAT II inhibition on neuropsychological test performance. We will use the following 7 tests from the MATRICS Consensus Cognitive Battery (27): Brief Assessment of Cognition in Schizophrenia (BACS), Symbol-Coding, Hopkins Verbal Learning Test-Revised (HVL-T-R), Brief Visuospatial Memory Test-Revised (BVMT-R), Continuous Performance Test-Identical Pairs (CPT-IP), Maryland Letter-Number Sequencing (LNS), and WMS®-III Spatial Span.

Clinical and Cognitive Assessment Training and Reliability: The MPRC provides resources for the conduct of training and interrater reliability procedures for the BPRS, SANS, CDS, and CGI. The clinical rater will be appropriately trained and meet required inter-rater reliability standards (ICC ≥ 0.80), before assignment as a rater. During the course of the study, interrater sessions for these assessments will be held every three months to maintain rater reliability and minimize rater drift. [name] will train the neuropsychological rater in the administration of the cognitive assessments.

Laboratory Assessments: The following laboratory assessments will be collected:

a) Kynureneine pathway metabolites: We will collect the following kynureneine pathway metabolites: kynureneine and KYNA. We will use high performance liquid chromatography to measure serum kynureneine and kynurenic acid levels. Perfusate samples will be diluted 1:2 for determination of both molecules. Plasma samples will be diluted 1:2 for kynureneine and 1:10 for KYNA determination. Twenty μ L will then be subjected to HPLC analyses and analytes will be detected fluorimetrically.

b) We will collect ~8mL of whole blood which will be transferred into a 10mL Cryovial cryogenic tube and placed in -80 freezer until time of analysis. Single-Nucleotide Polymorphism (SNP) genotyping will be performed on gDNA isolated from blood with QIAamp DNA Maxi Kit (Qiagen) using TaqMan polymerase chain reaction (PCR) technology.c) Two aliquots of blood will be stored at -80 until analyzed for inflammatory markers, oxidative stress, and other related markers.

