rates, height and weight), and a nicotine use questionnaire. We will also collect baseline EKG; CBC; complete metabolic panel, (including electrolytes, BUN/Creatinine, LFTs, lipid panel, and TSH); UA; expired CO, and Toxicology screen assessments. Female participants will have a pregnancy test during the Evaluation Phase and on each challenge test day. The Side Effect Checklist (SEC) is designed to assess medication side effects commonly associated with pharmacological treatments. The SEC version for the proposed study rates 32 potential side effects, and comprehensively covers the side effects that have been previously reported with NAC and TRYp administration, i.e., nausea, vomiting, diarrhea, abdominal pain, dizziness, dysgeusia, rash with or without fever, and sedation. In addition, there are three “other” spaces for idiosyncratic participant complaints, which are not usually associated with medication treatment. We will use the self-rated Stanford Sleepiness Scale (SSS) to supplement our assessment of sedation (45). The SSS is a 7-point Likert scale.

Study Procedures: Study Visit 1 will last about 3 hours, Study Visit 2 will last about 2 hours, and Visits 3 and 4 each will each last about 7.75 hours for a total study participation time of 20.5 hours.

Evaluation Phase (Visits 1 and 2): There will be a 2-week Evaluation Phase, during which potential participants will undergo baseline assessments to determine whether they meet inclusion criteria. Participants will be clinically stable, with clinical stability defined as two consecutive CGI ratings with no change in score.

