Challenge Phase (Visits 3 and 4): The Challenge Phase will utilize a double-blind, placebo-controlled, randomized cross-over design. A permuted block randomization system (block sizes 2 or 4) will be used to randomly assign participants to NAC, 140 mg/kg up to a maximum of 15 g, or placebo. There will be two Challenge Phase visits, which will be at least two weeks apart. On the day of each visit, participants will arrive at the MPRC Brief Stay Unit (BSU) at 7:15AM; all participants will have fasted since midnight. Participants are asked to avoid eating food of any kind after midnight the evening prior to visits 2 and 3. Participants are encouraged to drink water but to strictly avoid food, coffee, alcohol, and sodas. Participants who regularly use nicotine products will be given short breaks to use their products in order to avoid effects of nicotine withdrawal. The nicotine breaks will occur at least 60 minutes prior to the neuroimaging sessions in order to minimize the effect of nicotine on any of the neuroimaging measures. A heparin lock will be inserted for the repeated laboratory assessments and the initial clinical, cognitive, laboratory, and safety assessments will be conducted (including urine pregnancy test for female participants). Participants will then undergo their pre-treatment imaging studies. Upon completion of the imaging studies, participants will receive NAC, 140 mg/kg up to a maximum of 15 g, or placebo. They will receive the other study medication on the second visit (i.e., placebo or NAC). The proposed NAC dose has been used extensively to treat acetaminophen poisoning. We selected this high dose based on our preclinical studies showing high doses inhibit KAT II. There is extensive safety data available with this dose. We selected the effervescent formulation to minimize gastrointestinal and other side effects. In addition, the effervescent formulation is flavored, which helps to increase the tolerability and to mask the smell typically associated with NAC (46). Thirty minutes after NAC/placebo administration participants will receive TRYp, 6 grams in oral slurry form. The dose was chosen based on previous work showing cognitive effects to be associated with doses above 5 grams (47) and our the preliminary data from our previous Conte Center project, in which we demonstrated that TRYp (6 grams) produces a robust increase in KYNA and kynureine and reduction in the ASL measure of CBF in participants with schizophrenia and related disorders.

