Adherence: The NAC and placebo will be administered as dissolving tablets in a glass of 300 mL of water and the tryptophan will be given as a powder mixed with 150 mL of water. The participants will drink both mixtures in the presence of research staff.

Participant Payment: Participants will receive \$20 per hour and \$100 for the completion of each challenge day, for a total of approximately \$620. Participants will be paid by check, which may take up to 4-6 weeks to receive payment.

Management of Data: Data collected for this study will be entered into the MPRC research data base using the usual procedures developed for MPRC clinical trials. This study will be reviewed UMB IRB and by a Data Safety Monitoring Board (DSMB).

Data Analysis: Statistical analyses will be conducted using intent-to-treat analytic strategies. The overarching goal of our statistical approach is to identify the NAC versus placebo effects on measurements collected from

various biomedical assays, including peripheral KYNA (Specific Aim #1), ASL-CBF (Specific Aim #2), DTI FA and MRS measures (Specific Aim #3). The multilevel mixed effect model will be used to examine the NAC effects, while accounting for the hierarchical random effects that 1) each participant will have two Challenge Phase visit days; and 2) on each day longitudinal and/or multivariate measurements will be recorded (e.g. KYNA will be measured at different time points); the multilevel mixed model is compatible with unbalanced measurements. Taking Specific Aim #1 for example, the model will be KYNA ~ Treatment + covariates + randomEff-day/time. Adjustments for multiple testing will be performed when necessary. When the variance and covariance matrix is difficult to compute, the hierarchical Bayesian model will be implemented for parameter estimation via Markov Chain Monte Carlo (MCMC) sampling. With a sample size of 100 participants and 20% attrition rate (i.e., 60 participants will complete the study), we will achieve power > 80% for all three specific aims. In Exploratory Aim 1, we will perform mediation analysis to examine the NAC effects on cognitive measures via the changes in the central nervous system (neuroimaging measures as mediators). In Exploratory Aim 2, we will evaluate whether the baseline KMO and/or KYNA levels can moderate the NAC effects on the measures described in Specific Aims 1-3 (50).

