Specific Aim #1: Peripheral KYNA will be measured prior and after treatment on both Challenge Phase visit days (i.e., N-acetylcysteine (NAC) and placebo). We will denote the Challenge Phase visit day as $d=1,2$, and the multiple measurement times on each day by $t=1, \dots, T$ for each participant i ($i=1, \dots, 100$). To test the hypothesis whether NAC compared to placebo blocks the peripheral conversion of kynurenone to KYNA, we will apply the multilevel mixed model to compare the changes of KYNA levels from baseline between the two treatment groups. The hierarchical random effects will include day and time points within a day. With a sample size of 100 participants and 20% attrition rate (i.e., 60 participants will complete the study), we will achieve power 80% to detect a small-medium effect size of Cohen's d 0.37 at the alpha level 0.05. In our previous study, the effect size of peripheral KYNA change (tryptophan vs. placebo) is $d= 4.77$. Thus, we will have ample power to detect the difference. The covariates including age, sex, and others will be examined and adjusted when necessary.

Specific Aim #2: To examine whether NAC compared to placebo attenuates the effects of tryptophan on ASL CBF measures, we will apply the mixed model to compare the changes of ASL CBF levels from baseline between treatment and placebo. The primary ASL outcome measure will be whole brain gray matter CBF. If significant, then we will perform additional analyses to examine whether specific cortical regions show group differences. The multiple comparison correction will be performed for the voxel level and cluster level inference using permutation test-based strategy (51). With a sample size of 100 participants and 20% attrition rate (i.e., 60 participants will complete the study), we will achieve power 80% to detect a small-medium effect size of 0.37 at the alpha level 0.05. In our previous study, the effect size of ASL whole brain gray matter CBF (tryptophan vs. placebo) was Cohen's $d=0.48$. Thus, we should have sufficient power to detect the difference. The covariates including age, sex, and others will be examined and adjusted when necessary.

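### Aim 1 hypothesises reduced conversion of kynurenine to KYNA, but the only analysis described is change in KYNA level and no conversion measure is defined

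*Combined protocol and SAP*

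**What the plan says.** In the Specific Aim section, primary outcome 1 names both analytes: "we will measure serum kynureine and KYNA before and after NAC/placebo pre-treatment and TRYP administration". Its purpose is to "examine whether NAC compared to placebo blocks the peripheral conversion of kynureine to KYNA". Laboratory Assessments confirms that both are assayed: "We will collect the following kynureneine pathway metabolites: kynureneine and KYNA". The hypotheses that follow the aims use conversion a second time: the NAC effects on imaging are expected to be independent of glutathione change and "will be correlated with NAC-induced reductions in the peripheral conversion of kynurenine to KYNA".

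The Data Analysis section gives the Aim 1 model as an example: "the model will be KYNA ~ Treatment + covariates + randomEff-day/time". Under Specific Aim #1 it restates the conversion hypothesis and then says "we will apply the multilevel mixed model to compare the changes of KYNA levels from baseline between the two treatment groups". The covariates are age, sex and unnamed others. The section describes no kynurenine analysis and no ratio or other index of conversion.

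On dosing, Challenge Phase says "Thirty minutes after NAC/placebo administration participants will receive TRYp, 6 grams in oral slurry form". This applies on both days, and Adherence says that staff watch both mixtures being drunk.

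**The concern.** Serum KYNA depends on how much kynurenine is available as well as on how much of it is converted. The Specific Aim section itself says that the tryptophan challenge raises both analytes. A lower KYNA rise on the NAC day could therefore mean less conversion, less substrate or later arrival of substrate. In the other direction, higher kynurenine on the NAC day could hide a real fall in conversion.

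Aim 1 is the peripheral evidence for KAT II inhibition. It also supplies the variable meant to show that imaging effects follow KYNA rather than glutathione. With conversion undefined, the choice between KYNA alone, a ratio and kynurenine-adjusted KYNA could be made after the data are seen.

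**Working it through.** **Hypothesis against test.**

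| Item | Specific Aim and hypotheses | Data Analysis |
|---|---|---|
| Target | Conversion of kynurenine to KYNA | Change in KYNA level |
| Kynurenine | Part of primary outcome 1 | Not an outcome, denominator or named covariate |
| Conversion measure | Needed for Aim 1 and for the imaging correlations | Not defined |

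**The plan's own figure.** The inputs, from Specific Aim #1, are d = 0.37, alpha 0.05 and 60 completers. A two-sided paired t-test has noncentrality d√n = 0.37 × √60 = 2.87 on 59 df, which gives power 80.5% against the stated 80%. The same sentence gives 20% attrition from 100, which is 80 completers; at 80 the power is 90.5%. I use 60 because it reproduces the stated power. This power belongs to a generic d of 0.37. The cited d = 4.77 compares tryptophan with placebo on KYNA, and no SD is given for a conversion measure, so power for conversion cannot be computed.

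**Illustrative size.** Assume no inhibition, a KYNA rise proportional to substrate, and a fraction f of substrate lost on the NAC day. The apparent effect is then 4.77 × f in the units of whatever SD was used for 4.77, which the documents do not state.

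- If 4.77 shares the standardiser of 0.37, f = 5% gives d = 4.77 × 0.05 = 0.239, and Aim 1 is significant in 44% of trials (n = 60; 56% at n = 80). The loss that reaches d = 0.37 is 0.37/4.77 = 7.8%.
- If 4.77 is on a single-day SD, divide by √(2(1 − r)), where r is the between-day correlation. At r = 0, 0.239/1.414 = 0.169, significant in 25% of trials. At r = 0.8, 0.239/0.632 = 0.377, significant in 82%.
- If the same 5% mean loss is concentrated (shared standardiser, simulated), Aim 1 is significant in 30% of trials when 10% of participants lose half, and in 20% when 5% lose all.

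**Does a ratio solve it?** Only in part. By the procedures table, tryptophan is given at 11:05 and blood is drawn at 12:05, 1:35 and 3:05, that is 1, 2.5 and 4 hours later. Challenge Phase says that levels go on rising for about three hours, so the early samples are not at steady state. I took a simple first-order chain, gut to kynurenine to KYNA, with assumed rates (for instance absorption 1 per hour, kynurenine loss 0.3 to 0.7 per hour, KYNA turnover 0.7 to 3 per hour). A 30-minute absorption delay with conversion unchanged lowered mean log(KYNA/kynurenine) over the three samples by 0.06 to 0.18 across the assumptions tried. A true 10% inhibition is −ln(0.9) = 0.105. Mean log kynurenine moved only −0.06 to +0.04, because a lower first value is offset by later ones. The average over samples could therefore hide the delay, while the values sample by sample would tend to show it.

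**The case against.** The strongest defence is that substrate should be equal by design. Tryptophan is a fixed 6 g on both days, drunk under observation, and its own nausea and vomiting are common to both days. The Side Effect Checklist is repeated after dosing and "comprehensively covers the side effects that have been previously reported with NAC and TRYp administration". This stands as far as intake goes. It does not settle absorption: NAC is given half an hour before tryptophan, and Risks Related to N-acetylcysteine rates both vomiting and diarrhea as somewhat likely. The documents neither show nor exclude a substrate difference.

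A second defence is that the KYNA model is offered as an example, the covariate list is open, and kynurenine is part of primary outcome 1, so it would probably be reported. That is fair. The plan is under-specified; it does not rule kynurenine out. An open covariate list still prespecifies nothing.

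A reader might infer that NAC lowers kynurenine, or that a positive Aim 1 would be false. Nothing in the documents supports either. A reader might also take the percentages above as a worst case. They are not a bound, since they depend on an unstated standardiser and an assumed loss. Nor does a case such as 10% inhibition with kynurenine 10% higher measure how often an effect would be missed: 0.9 × 1.1 = 0.99, so the two cancel by construction. It shows only that masking is possible.

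**Conclusion.** The mismatch is real and should be fixed: the stated test does not isolate the stated hypothesis, although the data needed to address it are already collected. Confidence is high on that reading of the text, which depends on none of the figures.

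The size is not known. The 25% to 82% range assumes 60 completers, no inhibition, a proportional KYNA rise, a uniform 5% loss, and 4.77 on a single-day SD with between-day correlation from 0 to 0.8. It is 44% on the shared standardiser, and 20% to 30% there if few participants carry the loss.

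It is tempting to conclude that the ratio should replace KYNA as the Aim 1 outcome. The sampling times do not support that, because delayed absorption alone can lower the ratio. Confidence in the ratio as a measure of conversion is moderate.

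**What to change.** Before unblinding, add to Specific Aim #1 in the Data Analysis section:

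1. Keep the KYNA-level comparison as stated.
2. Prespecify log(KYNA/kynurenine), NAC versus placebo, adjusted for the same-day pre-dose ratio, as the conversion measure.
3. Report the ratio, kynurenine and KYNA by treatment at each of Laboratory Assessments 2, 3 and 4, and over the whole period (for example, the AUC of each analyte).
4. Tabulate checklist vomiting and diarrhea by treatment day.
5. State that lower KYNA without a lower ratio will not be read as KAT II inhibition, and that a lower ratio will be read with the kynurenine time course.
6. Use the same measure in the planned correlations with imaging.
7. Give KYNA adjusted for concurrent kynurenine as a sensitivity analysis only, because it conditions on a post-treatment variable and assay error in kynurenine leaves some substrate effect behind.

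The cost is SAP wording and a little more analysis, with no new sample, assay or visit. The ratio has drawbacks that the SAP should state: it carries two assay errors, it assumes proportionality, and it is sensitive to absorption timing, mainly at the earlier samples.

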
Two hours after ingestion of NAC/placebo, participants will undergo the post-treatment imaging studies. We chose to begin scanning 120 minutes after NAC and 90 minutes after TRYp, because 1) our preclinical data show that NAC administered 30 minutes prior to TRYp administration attenuates KYNA production through KAT II inhibition; 2) our preliminary data suggests that peripheral kynureine and KYNA levels are initially elevated 30 minutes after TRYp ingestion, and continue to increase over the next three hours and remain elevated for at least 3.5 hours; 3) NAC pharmacokinetic studies have demonstrated that peak serum levels occur within 90-150 minutes of administration and remain elevated for 4-6 hours (46,48); and 4) GSH, an indirect measure of NAC in the CNS, starts to elevate 50 minutes after NAC administration, reaches maximal elevation 90-110 minutes after oral NAC administration and remains elevated for at least 120 minutes (49). Thus, there should be sufficient time to complete the post-treatment MRI, clinical, laboratory, and cognitive assessments. A non-blind pharmacist will dispense all study medications. The blind will be broken

only if a medical emergency requires this information. If this occurs, the participant will be withdrawn from the study. The day after each challenge day, the RA will follow-up with the participant, via telephone, to evaluate whether there are any persistent effects from the receipt of the challenge medications. Any concerns of the participant will be reported immediately to the study physician.

Procedures/Assessments	Evaluation Phase (2 weeks)	Challenge Visit #1:	Challenge visit #2:	Initials
Informed Consent, Evaluation to Sign Consent	X			
Medical Screening: Medical History, physical exam, blood draw, urinalysis, toxicology screen, pregnancy test (females), EKG, medication use screening, caffeine use screening, Birth Control Selection (females)	X			
MRI screening	X			
Clinical Stability Determination (for participants with schizophrenia or a related disorder only): 2 unchanged CGIs	X			
Scheduling of challenge day visits	X			
Participant arrival at Brief Stay Unit (BSU) Review of Study Procedures		7:15 am	7:15 am	
Urine pregnancy (females); expired CO**; urine toxicology and breath alcohol testing		7:30 am	7:30 am	
Insertion of heparin lock		7:40 am	7:40 am	
Vital signs, SEC, SSS;		7:50 am	7:50 am	

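### The Aim 1 model names sampling time only as a random effect within day; without a fixed time factor, the shared post-tryptophan rise in KYNA can inflate the residual and cost power

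*Combined protocol and SAP*

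**What the plan says.** The Data Analysis section gives the Aim 1 model by way of example: "the model will be KYNA ~ Treatment + covariates + randomEff-day/time". Specific Aim #1 repeats the structure, "The hierarchical random effects will include day and time points within a day", and says that the model will "compare the changes of KYNA levels from baseline between the two treatment groups". The short formula shows KYNA itself, not its change. On covariates the text says: "The covariates including age, sex, and others will be examined and adjusted when necessary". Neither place names a fixed time or treatment-by-time term.

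The visit schedule has four blood samples per challenge day: 7:50 am, 12:05 pm, 1:35 pm and 3:05 pm. Tryptophan is given at 11:05 am on both days, so the last three samples fall 60, 150 and 240 minutes after it. The timing rationale in the Challenge Phase section says that kynurenine and KYNA are already raised at 30 minutes and "continue to increase over the next three hours and remain elevated for at least 3.5 hours".

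For fitting problems, Data Analysis adds: "When the variance and covariance matrix is difficult to compute, the hierarchical Bayesian model will be implemented for parameter estimation". For power, Specific Aim #1 says: "we will achieve power 80% to detect a small-medium effect size of Cohen's d 0.37 at the alpha level 0.05".

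**The concern.** Both challenge days include tryptophan, so every participant is expected to show a KYNA rise on each day. Its average shape is systematic and is not noise. If sampling time is only a random effect nested in participant and day, each cell of that nesting holds a single value. The time variance and the residual variance are then aliased, and the common trend has nowhere to go but the within-day error.

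A large within-day mean square can push the estimated participant-by-day variance to zero. The NAC standard error is then built partly from the tryptophan curve instead of from the day-to-day variation that governs a cross-over comparison. At stake is power on the first listed primary outcome. A missed effect there could be misread as evidence that NAC does not inhibit KAT II.

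**Working it through.** **1. The plan's own figure.** A paired t-test with n = 60, d = 0.37 and alpha 0.05 (two-sided assumed) has power 80.5%; the detectable d at 80% is 0.368. The stated 80% therefore reproduces as a simple paired calculation that does not use the mixed model. It takes 60 completers from "With a sample size of 100 participants and 20% attrition rate (i.e., 60 participants will complete the study"). A 20% loss from 100 leaves 80, for whom power would be 90.5%. That mismatch needs reconciling separately; 60 is used below.

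**2. Inputs.**
- From the documents: three post-dose samples per day; outcome is change from baseline; rise 4.77, the effect size for KYNA change, tryptophan versus placebo.
- Assumed: 4.77 is in SDs of change. Raw variances are participant 0.5, participant-by-day 0.3, residual 0.2. Several shapes of the rise are tried.

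**3. Change scale.** Subtracting the same-day pre-dose value cancels the participant and day components. The pre-dose error is shared by the three changes, so:
- day-level variance vd = 0.2 and within-day variance ve = 0.2;
- SD of a change = √0.4 = 0.632;
- rise R = 4.77 × 0.632 = 3.017, and R² = 9.10.

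All these terms scale with the residual variance, so the ratios in step 5 do not depend on the value 0.2.

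**4. Formulas (balanced data, no fixed time).**
- MS(within) = ve + SS(time)/2, where SS(time) = R² × the sum of squares of the three fractions about their mean.
- MS(day) = 3vd + ve = 0.8.
- If MS(within) ≤ MS(day), nothing is lost.
- Otherwise the day variance is estimated as zero, pooled MS = (4 × MS(within) + MS(day))/5, and the SE ratio r = √(pooled/MS(day)).
- Power ≈ Φ((1.960 + 0.842)/r − 1.960).

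**5. Results, by fraction of the maximum rise at 60/150/240 min.**

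| Curve | Fractions' SS | MS(within) | Pooled | r | Power |
|---|---|---|---|---|---|
| Linear from dosing to 210 min (29/71/100%) | 0.2585 | 1.376 | 1.261 | 1.26 | 61% |
| 40/80/100% | 0.1867 | 1.049 | 1.000 | 1.12 | 71% |
| 60/90/100% | 0.0867 | 0.594 | not pooled | 1.00 | 80% |
| 85/95/100% | 0.0117 | 0.253 | not pooled | 1.00 | 80% |

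If the participant variance of change is also estimated as zero, pooling runs over six mean squares. For the first row this gives (4 × 1.376 + 2 × 0.8)/6 = 1.184 and r = √(1.184/0.8) = 1.22; for the second, (4 × 1.049 + 1.6)/6 = 0.966 and r = 1.10.

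**6. Simulation.** A balanced cross-over with 60 completers and a near-linear rise was run under six assumed sets of variance components, with change from baseline as the outcome.
- At a 4.77 SD rise, the SE without fixed time was 1.20 to 1.32 times the SE with it. Power was 55-71% without and 75-84% with.
- At a 1 SD rise the ratio was 1.00 in every set.
- Over the 4.77 SD cells, raw and change outcomes together, type I error without fixed time was 0.000-0.048.
- In one data set fitted with a standard mixed-model routine, the NAC estimate was identical with and without time.

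**7. Aliasing.** The literal participant/day/time nesting, fitted to that data set, ended on the boundary with a Hessian that was not positive definite, as expected with one value per cell.

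**The case against.** The strongest reply is that the formula is shorthand, introduced as an example. The covariate list is open-ended, so a fixed time term is not excluded. If day/time means time effects common to all participants, the rise enters that variance component and not the error. Both points stand. They make the loss conditional, but two readable versions with different standard errors are themselves a reason to specify the model.

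Stronger readings are tempting and are not supported:
- *The standard error must be too wide.* Steps 5 and 6 show no loss for flatter curves or a small rise. Large day-to-day variance also protects. For the 40/80/100% curve with no participant variance in change, nothing is lost once 3vd ≥ 4.77² × 0.1867/2 × (vd + ve) = 2.124(vd + ve), that is, vd at or above about 2.4 times ve.
- *Power falls to about half or lower.* Reading 4.77 in raw SD units with the same variances (vd = 0.3, MS(day) = 1.10) gives r = 1.37 and 53% for the 40/80/100% curve. But the plan reports 4.77 for KYNA change. Analysing raw KYNA with the pre-dose sample included gave simulated ratios of 1.00 to 2.12, but Specific Aim #1 compares changes from baseline. A curve with no rise at 30 minutes would be worse still, and it contradicts the timing rationale.
- *The NAC effect would be biased.* Not in balanced data. A shift needs late samples to be missing more often on one treatment, which the documents do not predict.
- *The aliasing is the stated trigger for the Bayesian switch.* The trigger is only computational difficulty, and an aliased term can simply be dropped. The convergence failures seen were in one data set and one package.

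**Conclusion.** The point holds as a specification weakness with a conditional, conservative cost. As written, Aim 1 names sampling time only as a random effect; at participant level that term is aliased with the residual, and a shared trend can inflate the error. Under the assumptions above, the NAC standard error is about 1.0 to 1.3 times too wide and power with 60 completers is about 60-80% instead of 80%. The least favourable simulated set gave 55%, against 75% with time fixed.

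The size rests on variance components and curve shapes that the documents do not give, and on reading 4.77 as SDs of change. The 4.77 is used only to size the time trend; it says nothing about the NAC-versus-placebo effect. The loosely worded Bayesian switch is mostly missing detail and does not carry this point.

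**What to change.** In the Data Analysis and Specific Aim #1 text:
- State that the outcome is change from the same-day pre-dose value.
- Enter sampling time as a fixed categorical factor with a treatment-by-time term.
- Keep participant and participant-by-day as the random effects, and drop the aliased time-within-day term.
- Make the Aim 1 test the average post-dose NAC effect at the stated alpha.

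With three post-dose samples this adds about four fixed-effect parameters: two for time and two for treatment-by-time. It needs no new data and no change to the visits. Removing the aliased term also makes the Bayesian switch less likely to be reached. The plan should still say how computational difficulty will be judged.

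A paired NAC-minus-placebo analysis of mean post-dose change is useful as a sensitivity check, since it matches the plan's power calculation. It should not be the primary analysis or the fallback, because it drops anyone with a missing day. That sits badly with the plan's intent-to-treat statement and its reason for choosing a mixed model.
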